4.6.2.2 Sensitivity Analysis

4.6.2.2.1 Sensitivity analysis 1 – Control-based MI

To assess the robustness of the main analysis results based on MAR assumption, a sensitivity analysis based on MI for missing serum bile acid result at each scheduled visit will be conducted.

The MI procedures that described for the primary endpoint in [section 4.5.2.2.1](#) will be applied.

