4.5.2.2 Sensitivity Analyses

4.5.2.2.1 Sensitivity analysis 1 – Control-based MI

To assess the robustness of the primary analysis results based on MAR assumption, a sensitivity analysis based on MI for missing average AM and PM monthly scratching scores will be conducted.

The following procedures in MI will be followed:

1. Intermediate missing values are imputed by the Markov Chain Monte Carlo (MCMC) imputation model, so only monotone missing values exist after imputation. Only imputed values within the range of 0 to 4 will be used since the rating of the questionnaire is from 0 to 4.
2. The monotone missing values are imputed chronologically by month using SAS Proc MI regression method including baseline age stratification and baseline direct bilirubin in the model. For all patients with missing average scratching score for any reason, their missing average scratching score will be imputed from all placebo patients in a visit-by-visit (i.e., Month by Month) manner, regardless of study treatment assignment. This is done by each imputed data set from step 1. Only imputed values within the range of 0 to 4 will be used.
3. After the imputation, all data are pooled and the MMRM analysis is performed on each of the 200 imputed datasets.
4. The same MMRM model as in the primary analysis is used to compare the treatment effect at Month 6 (Weeks 21 to 24). This is done by the imputation IDs from step 1.
5. The results from step 4 will be combined using Rubin's method [14].

4.5.2.2.2 *Sensitivity analysis 2 - Tipping point analysis*

A tipping-point analysis will be used to explore whether missing data could have adversely impacted findings from the analysis of change from baseline in scratching score to Month 6 (Weeks 21 to 24) regardless of treatment adherence. The goal of a tipping-point analysis is to explore how the overall results may be impacted by different assumptions about the magnitude of change from baseline in scratching score to Month 6 (Weeks 21 to 24) for those with missing Month 6 (Weeks 21 to 24) data, which are sensitivity parameters (defined for each treatment group) that are systematically varied.

The tipping-point analysis will be implemented as follows:

1. 100 imputed datasets will be created using multiple imputation (MI) based on MAR, the same steps 1-2 in section 4.5.2.2.1 will be used to impute the missing average AM and PM score except that in step 2 the imputation will be done within each treatment group.

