2. At each missing visit, the baseline score will be subtracted from imputed score to obtain imputed change from baseline (CHG).
3. For each patient with a missing Month 6 (Weeks 21 to 24) value, the following steps will be performed for adjusting the imputed CHG with mean zero and add the constant for the tipping steps:
 - a. The average imputed CHG will be computed based on the 100 imputed datasets from step 2 per patient.
 - b. The average imputed CHG will be subtracted from the imputed CHG per subject per imputed dataset and this is resulting in the imputed CHG among the imputed datasets for a subject having a mean of zero at month 6.
 - c. A constant ΔO and ΔP will be added to the imputed value for the odevixibat arm and the placebo arm for each of the imputed datasets.
4. Combine imputed CHG at month 6 in step 3 and other visit in step 2 with the observed CHG to get the completed 100 datasets for analyses in step 4 and 5.

5. Results from the same MMRM model as used in the primary analysis fit to the imputed datasets will be combined using Rubin's method [14]. Treatment effect estimates, p-value and limits from the 95% confidence interval (CI) will be retained.
6. The above steps will be repeated, using different values for ΔO and ΔP .

To characterize the extent of departures from assumptions that change the interpretation of the results in terms of their statistical or clinical significance, with particular interest to identify the region in the sensitivity parameter space that leads the results to no longer be statistically significant, a map of treatment effects and p-values obtained in Step 6 above will also be presented, so as to allow assessment of the differences in posited scenarios for missing outcomes, that would lead to a change in conclusion from the study results.

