4.6.2.2.2 Sensitivity analysis 2 – Tipping point analysis

The analysis approach that described for the primary endpoint in [section 4.5.2.2.2](#) will be applied.

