4.6.2.3 Supplementary Analysis

4.6.2.3.1 Supplementary analysis 1 – Non-parametric analysis

The serum bile acid levels are expected to fluctuate. To evaluate the robustness of the deviation from the normal and homoscedastic assumptions used in the main analysis, a rank transform ANCOVA model with baseline age stratification, baseline serum bile acid, treatment group will also be used to evaluate the treatment effect. The ranked ANCOVA method permits adjustment for baseline values which increases the efficiency of the statistical test. Change from baseline to the average of Week 20 and Week 24 will be ranked ignoring treatment group. The value of mid-ranks will be used in the case of ties. The baseline serum bile acid data will also be ranked in the same manner. This analysis will be performed with missing data at each scheduled visit imputed by MI based on MAR (the step 1 in the tipping point analysis) before ranking. The multiple estimates of treatment difference from the ranked ANCOVA will then be combined using Rubin's rules. The same ranked ANCOVA will also be performed at each visit (Weeks 4, 8, 12, 16, 20, 24).

4.6.2.3.2 *Supplementary analysis 2 – Based on the PP analysis set*

The MMRM utilized for the main analysis in [section 4.6.2.1](#) will also be used for the PP analysis set.

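### All three imputation-based bile acid analyses inherit the scratching score's 0–4 limit by cross-reference, and two of them also inherit its Month 6 target

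*SAP*

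**What the plan says.** The imputation rules are written once, for the scratching score, in SAP 4.5.2.2.1 and 4.5.2.2.2.

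- **4.5.2.2.1, step 1** (the limit is repeated in step 2): "Only imputed values within the range of 0 to 4 will be used since the rating of the questionnaire is from 0 to 4".
- **4.5.2.2.1, step 4:** "The same MMRM model as in the primary analysis is used to compare the treatment effect at Month 6 (Weeks 21 to 24".
- **4.5.2.2.2, step 1:** "the same steps 1-2 in section 4.5.2.2.1 will be used to impute the missing average AM and PM score", except that step 2 is run within each arm.
- **4.5.2.2.2, step 3:** "For each patient with a missing Month 6 (Weeks 21 to 24) value, the following steps will be performed"; the steps are re-centring the imputed change to mean zero and adding an arm-specific constant.

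The bile acid sections point back to these rules.

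- **4.6.2.2.1 (control-based MI):** "a sensitivity analysis based on MI for missing serum bile acid result at each scheduled visit will be conducted"; for the method, "The MI procedures that described for the primary endpoint in" section 4.5.2.2.1 are to be applied.
- **4.6.2.2.2 (tipping point):** one sentence, beginning "The analysis approach that described for the primary endpoint in" section 4.5.2.2.2.
- **4.6.2.3.1 (ranked ANCOVA):** missing visits are imputed by "the step 1 in the tipping point analysis) before ranking". This section names its own target, the Week 20/Week 24 average, and adds each visit.

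SAP 4.6.2.1 defines the main bile acid comparison as the Week 20/Week 24 average. SAP Appendix 8 lists bile acid in µmol/L or µg/mL. Protocol 7.2.1, criterion 3, requires a value above the upper limit of normal at both screening visits.

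**The concern.** A 0–4 limit makes sense for a rating that runs from 0 to 4. It does not make sense for a concentration that is raised by eligibility. Table 3 lists four sensitivity and supplementary analyses for the key secondary endpoint, and three of them rest on this imputation; only the per-protocol MMRM does not. This is the only endpoint besides the primary that is tested under alpha control. If the text is followed literally, its missing-data analyses either cannot be run or are run on values that no enrolled patient would plausibly have, so they would not test robustness.

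The Month 6 wording is a second gap. Bile acid has no Month 6 score; it has Week 20 and Week 24 values that are averaged. In the tipping point it is left open whether the shift goes on Week 20, Week 24 or both, and that choice changes the map of results.

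**Working it through.** **1. The plan's own figures.** SAP 2.1 gives 45 randomized, 20% drop-out and 36 completers: 45 × (1 − 0.20) = 36, so 9 missing. With 24 and 12 completers, difference 1.2, SD 1.0 and 1-sided alpha 0.025, the noncentrality is 1.2 × √(24 × 12 / 36) = 3.39 on 34 degrees of freedom. The power is 0.9094, against 0.909 stated. These figures reproduce and are not in dispute; the drop-out rate is reused in step 4.

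**2. The chain of references.**

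| Bile acid analysis | Route to the rule | 0–4 limit inherited | Month 6 target inherited |
|---|---|---|---|
| Control-based MI, 4.6.2.2.1 | 4.5.2.2.1 directly | Yes | Yes, step 4 |
| Tipping point, 4.6.2.2.2 | 4.5.2.2.2 step 1, then 4.5.2.2.1 steps 1–2 | Yes | Yes, step 3 |
| Ranked ANCOVA, 4.6.2.3.1 | Tipping-point step 1, then 4.5.2.2.1 steps 1–2 | Yes | No, names its own target |

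The only general adaptation sentence, at the head of SAP Appendix 6, covers model covariates. It gives no range and no visit.

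**3. If draws outside 0–4 are rejected.** The documents give no bile acid mean, SD or upper limit of normal, so these inputs are assumptions. For a normal draw with mean M and SD s, the share kept is Φ((4 − M)/s) − Φ((0 − M)/s). For example, M = 100 and s = 100 give Φ(−0.96) − Φ(−1.00) = 0.99%.

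| Mean (µmol/L) | SD 30% of mean | SD 50% | SD 80% | SD 100% |
|---|---|---|---|---|
| 20 | 0.34% | 3.2% | 5.3% | 5.3% |
| 50 | 0.065% | 1.0% | 1.9% | 2.0% |
| 100 | 0.026% | 0.47% | 0.94% | 0.99% |
| 300 | 0.007% | 0.15% | 0.31% | 0.33% |

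The share kept runs from 0.007% to 5.3%, so about 95% or more of draws are rejected.

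**4. If values are forced into 0–4.** With 20% of an arm missing, its mean falls by 0.20 × (M − 4) to 0.20 × M: 9.2 to 10 µmol/L at M = 50, and 59.2 to 60 at M = 300.

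In the control-based MI both arms' missing values should sit near the placebo mean. The error in the treatment difference is therefore roughly −(fraction missing on odevixibat − fraction missing on placebo) × placebo mean. It cancels when the fractions are equal. An illustrative simulation agrees. It used 30:15 patients, an effect of 1.2 SD, a baseline mean of 2 SD, 9 missing, a single-landmark ANCOVA, and a non-negative bound as the intended rule.

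| Missing odevixibat/placebo | Intended (SD units) | Limited to 0–4 |
|---|---|---|
| 9/0 | −0.67 | −1.31 |
| 6/3 (equal fractions) | −0.83 | −0.83 |
| 3/6 | −0.98 | −0.32 |

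The formula gives −(0.30 − 0) × 2 = −0.60 for the first row, against a simulated shift of −1.31 − (−0.67) = −0.64.

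The ranked ANCOVA imputes within arm, so forcing both arms to nearly the same low value dilutes the contrast even at equal fractions. In the tipping point, re-centring removes the wrong location at the shifted visit but not the wrong spread: values close to uniform on 0–4 have SD 4/√12 = 1.15 µmol/L.

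**5. The shifted visit.** The endpoint is A = (W20 + W24)/2. A shift Δ on Week 24 alone moves A by Δ/2. For a patient missing both visits, shifting both moves A by Δ. A patient missing only Week 20 would get no shift at all under a last-visit rule.

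**The case against.** The best reply is that the 0–4 rule carries its own scope. Step 1 gives the questionnaire scale as its reason, and the SAP version history files the rule under 4.5.2.2.1 and 5.6. A competent programmer would see that it cannot apply to a concentration. That stands as evidence of intent. It does not supply the replacement: a floor at zero, no bound, or a transformed scale all remain open.

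It is also fair that the MI sample code in Appendix 6 is redacted, so a bile acid setting there can be neither confirmed nor excluded. The point is therefore limited to the readable text.

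The contrast is partly covered as well. SAP 4.6.2.2.1 sets out to test the main analysis, which 4.6.2.1 defines on the Week 20/Week 24 average. That leaves the tipping-point shift as the sharper gap.

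A reader might infer more than the documents support:

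- **That all three analyses borrow Month 6.** The ranked ANCOVA names its own target.
- **That bile acid has no visit rule at all.** Both 4.6.2.2.1 and 4.6.2.3.1 impute at each scheduled visit.
- **That the simulated biases forecast the trial's results.** They rest on assumed bile acid values and a single-landmark model rather than visit-by-visit imputation with an MMRM. They also cover only the case in which values are forced into 0–4. In the rejection case the analysis would be more likely to fail visibly than to report a biased figure.

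**Conclusion.** The point holds for the sensitivity and supplementary analyses only. On the readable text, three of the four such analyses in Table 3 inherit an imputation limit that cannot suit bile acid, and two inherit a target that is not the endpoint. Read literally, the limit is wrong, not just thinly specified: about 95% or more of draws fall outside it for assumed means of 20 to 300 µmol/L and SDs of 30% to 100% of the mean. If values were forced inside it instead, the direction of the error in the control-based MI would depend on which arm had the larger fraction missing. A shift placed on the last visit alone would move the averaged endpoint by half the nominal amount, so the tipping point would not fully stress it.

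The documents do not support the inference that the key secondary result itself is at risk. Its MMRM uses no imputation, and none of these analyses enters the testing hierarchy in SAP 4.7. The textual finding does not depend on any assumed bile acid value.

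**What to change.** Amend the SAP before database lock:

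- In 4.5.2.2.1, state that the 0–4 limit applies to scratching scores only.
- In 4.6.2.2.1, 4.6.2.2.2 and 4.6.2.3.1, state a limit suited to bile acid, for example non-negative with no upper bound.
- In 4.6.2.2.2, state that the re-centring and the shift apply to each missing Week 20 or Week 24 value.
- In 4.6.2.2.1 and 4.6.2.2.2, state that the 4.6.2.1 model is fitted and that the contrast is the Week 20/Week 24 average.

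The cost is a few lines of text and matching program settings. No new data are needed, and the confirmatory model, alpha and sample size do not change.

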4.6.2.2.2 Sensitivity analysis 2 – Tipping point analysis

The analysis approach that described for the primary endpoint in [section 4.5.2.2.2](#) will be applied.

4.6.2.3 Supplementary Analysis

4.6.2.3.1 Supplementary analysis 1 – Non-parametric analysis

The serum bile acid levels are expected to fluctuate. To evaluate the robustness of the deviation from the normal and homoscedastic assumptions used in the main analysis, a rank transform ANCOVA model with baseline age stratification, baseline serum bile acid, treatment group will also be used to evaluate the treatment effect. The ranked ANCOVA method permits adjustment for baseline values which increases the efficiency of the statistical test. Change from baseline to the average of Week 20 and Week 24 will be ranked ignoring treatment group. The value of mid-ranks will be used in the case of ties. The baseline serum bile acid data will also be ranked in the same manner. This analysis will be performed with missing data at each scheduled visit imputed by MI based on MAR (the step 1 in the tipping point analysis) before ranking. The multiple estimates of treatment difference from the ranked ANCOVA will then be combined using Rubin's rules. The same ranked ANCOVA will also be performed at each visit (Weeks 4, 8, 12, 16, 20, 24).

4.6.2.3.2 *Supplementary analysis 2 – Based on the PP analysis set*

The MMRM utilized for the main analysis in [section 4.6.2.1](#) will also be used for the PP analysis set.

4.6.3 Subgroup Analyses

The following subgroup analyses will be performed by using MMRM model with baseline serum bile acid, treatment group, visit and treatment-by-visit interaction. The approach to selection of the covariance matrix in the model will follow the same approach as for the primary endpoint.

- Age group 1: 0 to <10 and 10 to <18 years (Based on the actual age)
- Age group 2: 0 to <2, 2 to <12, 12 to <18 years (Based on the actual age)
- Region (US, EU, and RoW)
- Sex
- Race (White vs. Non-White (including race as not reported))
- Ethnicity (Hispanic or Latino (including ethnicity as not reported), Not Hispanic or Latino)
- Baseline serum bile acid (\geq median and $<$ median)
- The use of UDCA (Y, N)
- The use of anti-pruritus medication (Y, N)
- Child-Pugh classification (Class A, B, C)
- Hepatic impairment classification (no impairment, mild, moderate, or severe)
- Baseline direct bilirubin (>3 and ≤ 3 mg/dL and equivalent to >51.3 and ≤ 51.3 $\mu\text{mol/L}$)
- Genetic Testing for ALGS (JAG1 vs NOTCH2)

A forest plot of the subgroup analyses will be provided for the key secondary endpoint. Statistical analysis will be performed only when the sample size is ≥ 5 in each treatment group. If the sample size is < 5 in either treatment group, only summary statistics will be provided; the p-value will not be reported.

4.6.4 Other Secondary Endpoints

For all secondary endpoints, all data collected through the end of the study following an ICE due to premature discontinuation of study treatment prior to Week 24 (i.e., treatment policy strategy), will be included while excluding data following ICEs of biliary diversion surgery or liver transplant (i.e., hypothetical strategy).

The change in secondary endpoints such as serum bile acids, ALT, AST, gamma-glutamyl transferase, direct bilirubin, total bilirubin, total cholesterol, PRO and ObsRO sleep parameters will be summarized by visit using descriptive statistics.

In addition to evaluate vital signs (height and weight) in the safety analysis, growth data (height/length for age, weight for age, and BMI for age) will be considered as an exploratory efficacy endpoint. Growth data will be calculated using the software or methods from the Centers for Disease Control and Prevention (CDC) website [12] for patients with age ≥ 2 years old and from the World Health Organization (WHO) website [13] for patients with age < 2 years old.

Change from baseline in growth (i.e., height [cm], weight [kg], BMI [kg/m²] and corresponding linear growth compared to a standard growth curve [Z-score, SD from P50 standard growth curve], calculated by using the software or methods from the CDC website for patients with age \geq 2 years old and from the WHO website for patients with age $<$ 2 years old) will be summarized by visit using descriptive statistics.

4.6.4.1 Continuous Endpoints

Change in ALT, AST, gamma-glutamyl transferase, direct, total bilirubin and total cholesterol, change in itching score to Month 6 (Weeks 21 to 24) as measured by the Albireo PRO instrument, change in sleep parameters, and change in growth will also be analyzed using the MMRM model. The summary of change from baseline based on MMRM model will also be displayed using graphical presentations except for itching score as measured by the Albireo PRO instrument. MMRM model will include the baseline value of the response variable, baseline age stratification, baseline direct bilirubin (for change in itching score), treatment group, visit (in months for itching score and sleep parameters, and in weeks for other assessments) and treatment-by-visit interaction. The approach to selection of the covariance matrix in the model will follow the same approach as for the primary endpoint.

The change from baseline through Week 24 in the Albireo ObsRO scratching severity scores and PRO itching scores for the morning assessment, evening assessment, and average morning and evening assessment will also be evaluated by weekly score. These endpoints will be assessed combining age groups and by age group (based on the actual age), 0 to $<$ 8, 8 to $<$ 12, and 12 to $<$ 18. A line graph of scratching daily severity scores (average AM and PM) from the Albireo ObsRO and sBA over time for each patient will be provided. In addition, line plot for mean of change from baseline on Albireo ObsRO average AM and PM, AM, and PM scratching weekly score will be provided, respectively.

Patients (\geq 5 years) and caregivers will be asked to complete a quality-of-life questionnaire (PedsQL) at Randomization Day 1, Week 12, and Week 24. Details of the questions included on the questionnaire are provided in Protocol Appendix 4. Comparisons of the change from baseline at Week 12 and Week 24 in the PedsQL total score (calculated as average score of all answered items) and domain scores between the treatment groups will be conducted using ANCOVA. The model will include terms for baseline, age category based on the age groups defined for the PedsQL (5 to $<$ 8, 8 to $<$ 13, 13 to $<$ 18) and treatment. The analysis will be conducted based on the total scores reported by child (\geq 5 years of age) and by parent (including patients for all age) separately. If the sample size based on child reported data (\geq 5 years of age) is less than 10, then ANCOVA will not be conducted. The PedsQL total score and domain scores of the family impact module will be analyzed similarly.

A Pearson correlation coefficient will be provided to evaluate the relationship between the primary endpoint (change from baseline in scratching score to Month 6 (Weeks 21 to 24)) and the key secondary endpoint (change in serum bile acid levels from baseline to the average of Week 20 and Week 24).

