#### **9.1.3 Secondary Efficacy Endpoints:**

- Change from baseline in pruritus to Month 6 (Weeks 21 to 24) as measured by the Albireo PRO instrument
- Percentage of patients achieving a clinically meaningful decrease in pruritus (pruritus responders) as measured by the Albireo ObsRO/PRO instruments
- Change from baseline through Week 24 in patient reported and observer reported itching and scratching severity scores, respectively, for the morning assessment, for the evening assessment. These endpoints will be assessed combining age groups, and by age group, 0 to <8, 8 to <12, 12 to <18, and 18 years and over
- Change from baseline to Week 24 in sleep parameters as measured with the Albireo ObsRO/PRO instruments (e.g. tiredness and number of awakenings)
- Change from baseline to Week 24 in PedsQL subdomain scores
- Assessment of Global Symptom Relief to from baseline to Weeks 4, 12, and 24 as measured by patient, caregiver, and clinician GIS (PGIS, CaGIS, CGIS) items
- Assessment of Global Symptom Relief as measured by patient, caregiver, and clinician GIC (PGIC, CaGIC, CGIC) items at Weeks 4, 12, and 24
- Patient impression of treatment effect as recorded during exit interviews at Week 24
- Change from baseline to Week 24 in xanthomatosis as assessed by the Clinician Xanthoma Scale
- Change in serum bile acid levels from baseline through Week 24
- Change from baseline to Week 24 in serum ALT concentration
- Change from baseline to Week 24 in serum AST concentration
- Change from baseline to Week 24 in gamma-glutamyl transferase concentration
- Change from baseline to Week 24 in total bilirubin concentration
- Change from baseline in biochemical markers and measures of bile acid synthesis (autotaxin, p-C4, only in patients >10 kg)

- Change from baseline in total cholesterol concentration

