### **11.2.2.2 Missing Data**

There will be no imputation in the primary analyses of endpoints in this study as methods robust to missing data such as the mixed-effect model for repeated measures (MMRM) will be used. Each week, at least 4 of 7 assessments need to be completed for each of the AM and PM assessments. If these minimum assessments are not available, the week is considered missing. Monthly values will only be calculated if at least 3 weeks can be calculated. Sensitivity analyses including multiple imputation for missing data will be employed to assess the robustness of efficacy results and will be specified in the Statistical Analysis Plan.

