#### **11.2.2.7 Evaluation of Additional Efficacy Variables**

There will be no alpha adjustment for multiple hypothesis testing as these additional efficacy variables are supportive, only. For efficacy variables in which change from baseline is assessed, MMRM will be used as the primary analysis methodology in the FAS population. Sensitivity analyses will be performed as defined in the Statistical Analysis Plan.

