4.6.4.3 Biomarkers

Blood samples for autotaxin and p-C4 will be drawn at randomization (Study Day 1), Week 12, and Week 24, only for children with body weight >10 kg. For biochemical markers and measures of bile acid synthesis, the change from baseline to Week 24 will be analyzed descriptively in addition to the actual visit values.

FGF-19 is collected when a patient meets criteria for close observation due to suspected drug-induced liver injury (DILI); the results will be provided in a listing.

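### The SAP replaces the protocol's MMRM with by-visit ANCOVA for PedsQL and with description alone for autotaxin and p-C4, and declares neither change

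*SAP*

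**What the plan says.** Protocol 11.2.2.7 sets one rule for the additional efficacy variables: "For efficacy variables in which change from baseline is assessed, MMRM will be used as the primary analysis methodology in the FAS population". Protocol 9.1.3 puts PedsQL and the two markers under that rule. Its secondary efficacy endpoints include "Change from baseline to Week 24 in PedsQL subdomain scores" and "Change from baseline in biochemical markers and measures of bile acid synthesis (autotaxin, p-C4, only in patients >10 kg".

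Protocol 11.2.2.2 ties the missing-data policy to the same method: "There will be no imputation in the primary analyses of endpoints in this study as methods robust to missing data such as the" MMRM are planned.

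The SAP does three different things:

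- **Most continuous secondary endpoints (4.6.4.1).** Liver tests, cholesterol and PRO itching are modelled by MMRM, and "change in sleep parameters, and change in growth will also be analyzed using the MMRM model".
- **PedsQL (4.6.4.1).** Respondents complete the "quality-of-life questionnaire (PedsQL) at Randomization Day 1, Week 12, and Week 24". Comparisons of the total score and "domain scores between the treatment groups will be conducted using ANCOVA", with baseline, PedsQL age category and treatment as terms. No imputation is mentioned.
- **Autotaxin and p-C4 (4.6.4.3).** For these, "the change from baseline to Week 24 will be analyzed descriptively in addition to the actual visit values". No model and no treatment comparison is given.

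Table 8 in SAP Appendix 1 lists four changes: the per-protocol set, direct bilirubin as covariate, least-squares-mean differences in place of a contrast statement, and growth as an added endpoint. Neither PedsQL nor the markers appear there or in the SAP version history.

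**The concern.** The protocol does without imputation because its models use all observed visits. Once PedsQL moves to a separate ANCOVA at each visit, that reason no longer covers it, and nothing replaces it. A Week 24 ANCOVA without imputation uses only children with a Week 24 value, so it ignores the Week 12 value of a child who has none. The SAP handles this differently elsewhere: the rank ANCOVA for serum bile acids (4.6.2.3.1) is run only after multiple imputation under MAR.

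At stake are some precision, possible bias if dropout is informative, and a planned comparison that is absent for two markers. It is also odd that growth, an exploratory endpoint added by the SAP, receives MMRM while endpoints named in the protocol do not.

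**Working it through.** **1. The plan's own figures.** 45 × (1 − 0.20) = 36 completers, 24:12 at 2:1. Exact two-sample t power with difference 1.2, SD 1.0 and 1-sided 0.025 is 0.9094, which matches the stated 0.909. These figures concern the primary endpoint. The documents give no power, SD or effect for PedsQL or the markers, so the inputs in steps 4 and 5 are assumptions.

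**2. The passages side by side.**

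| Endpoint | Protocol 11.2.2.7 | SAP | Listed in Appendix 1? |
|---|---|---|---|
| PedsQL change | MMRM | ANCOVA at each visit | No |
| Autotaxin, p-C4 change | MMRM | Descriptive | No |

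**3. Which PedsQL data are ignored.** SAP Table 10.2 assigns Day 57 to 126 to Week 12. It assigns Day 127 to EOS to Week 24 (to the day before EOS for children who do not roll over). An early-termination form from Day 127 on therefore counts as Week 24. One from Day 57 to 126 counts as Week 12, and if the child then leaves, the Week 24 ANCOVA does not use it. A child who leaves before Day 57 has neither value and adds nothing under either method.

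**4. Precision at Week 24.** Let m be the share missing Week 24, q the share of those with Week 12 data, and ρ the Week 12/Week 24 residual correlation. In large samples, with dropout unrelated to the scores:

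Var(MMRM) / Var(ANCOVA) = 1 − ρ²·qm / (1 − m + qm)

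Example: m = 0.20, q = 1, ρ = 0.5 gives 1 − 0.25 × 0.20 = 0.95, and 1/√0.95 = 1.026.

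| Excess SE of ANCOVA | ρ = 0.3 | ρ = 0.5 | ρ = 0.7 | ρ = 0.8 |
|---|---|---|---|---|
| m = 0.20, q = 1 | 0.9% | 2.6% | 5.3% | 7.1% |
| m = 0.20, q = 0.5 | 0.5% | 1.4% | 2.8% | 3.8% |
| m = 0.05, q = 1 | 0.2% | 0.6% | 1.2% | 1.6% |

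At Week 12 there is no gain under monotone dropout.

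**5. Bias at Week 24.** Simulation of 30:15 trials, 4,000 runs per setting, true Week 24 effect 0.70 residual SD, ρ = 0.5 / 0.7. MMRM was computed as the maximum-likelihood estimate for monotone two-visit data.

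| Assumed dropout mechanism | Missing | ANCOVA bias | MMRM bias | SE ratio, ANCOVA/MMRM |
|---|---|---|---|---|
| Completely at random | 20% | −0.011 / −0.010 | −0.012 / −0.012 | 1.022 / 1.052 |
| Poor Week 12 score, alike in both arms | 22% | −0.051 / −0.071 | −0.002 / −0.004 | 1.015 / 1.011 |
| Poor Week 12 score in placebo only | 19% | −0.151 / −0.206 | −0.004 / 0.002 | 1.006 / 1.031 |
| Opposite directions in the two arms | 22% | −0.245 / −0.338 | −0.002 / 0.003 | 0.977 / 0.980 |

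In the second row the loss is 0.051/0.70 = 7% to 0.071/0.70 = 10% of the effect. Where dropout depends on the score, MMRM's precision advantage shrinks or reverses; its benefit there is the removal of bias. All mechanisms in the table are MAR, so the table does not show how MMRM behaves when data are missing not at random.

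**6. The markers.** No between-arm estimate is specified, so steps 4 and 5 do not apply to them.

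**7. The age term.** The parent-report analysis includes all ages, but the PedsQL age categories in the ANCOVA are 5 to <8, 8 to <13 and 13 to <18. Children under 5 have no level. The randomisation stratum (<10, 10 to <18), used in the SAP's other MMRMs, covers every child.

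**The case against.** The strongest reply is that little is lost. ANCOVA adjusted for baseline is a legitimate method with two post-baseline visits. The SAP does not describe it as complete-case; that is an inference from the absence of any imputation. Early-termination forms from Day 127 count as Week 24, Protocol 7.1.4 asks that visits continue after treatment stops, and SAP 4.6.4 includes those data. A reader might infer that the planned 20% dropout is the share of PedsQL missing at Week 24. The documents do not say so, and the true share may well be smaller. The protocol calls these variables supportive, and they lie outside the alpha hierarchy (SAP 4.7).

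All of this stands, and it limits the size of the point. It does not remove the contradiction between protocol and SAP, or the lack of any stated reason for it.

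A reader might also infer that every other continuous endpoint in SAP 4.6.4.1 has an MMRM. That goes too far: the weekly morning and evening scores are to be evaluated with no model named.

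**Conclusion.** The departure from Protocol 11.2.2.7 is real for both PedsQL and autotaxin/p-C4, and it is undeclared.

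For PedsQL the cost is a Week 24 standard error about 1% to 7% larger at 20% missing with ρ from 0.3 to 0.8, about half that if only half of the affected children have Week 12 data, and at most 1.6% at 5% missing. Bias is conditional: about zero if dropout is unrelated to post-baseline scores, about 0.05 to 0.07 SD toward no effect if dependence is alike in both arms, and more if it differs by arm. MMRM removes this bias only under MAR. Correlation, effect and dropout mechanism are all assumed.

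It is tempting to conclude that ANCOVA will discard the worst outcomes, mostly from placebo, and so understate the benefit. Nothing in the documents says which arm will lose more children or why, so that is a scenario and not a finding.

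For autotaxin and p-C4 the defect is the absent treatment comparison, not lost precision. Primary and key secondary conclusions are unaffected. This is an inexpensive improvement that should be made.

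**What to change.** Before unblinding, amend SAP 4.6.4.1 and 4.6.4.3:

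- Analyse PedsQL total and domain scores, and separately autotaxin and p-C4, by MMRM with visits Week 12 and Week 24. Terms: baseline value, randomisation age stratum, treatment, visit and treatment-by-visit. Report the Week 24 contrast.
- Use the covariance sequence already in SAP 4.5.2.1: unstructured, Toeplitz, AR(1), compound symmetry.
- Keep the rule that no model is fitted to child-reported PedsQL data from fewer than 10 children.
- Keep the ANCOVA and the descriptive summaries as supportive results.

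If the sponsor prefers its present methods, the minimum is to list and justify both departures in Appendix 1.

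The cost is SAP wording and reuse of existing MMRM code, with no new data. The downside is slightly more modelling in a small sample and the replacement of the PedsQL age categories in the main model.
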